5.2.2 Panel B, Panel C, and Panel D (Participants with Schizophrenia) Exclusion Criteria

Participants are excluded from the study if any of the following criteria apply:

Medical Conditions

28. Has evidence or history of a primary DSM-5 axis I psychiatric diagnosis other than schizophrenia or schizoaffective disorder per the allowed DSM-5 criteria within one month of screening.
29. Has evidence or history of mental retardation, borderline personality disorder, anxiety disorder, or organic brain syndrome.
30. Has a history of neuroleptic malignant syndrome or moderate to severe tardive dyskinesia (TD).
31. Has a substance-induced psychotic disorder or behavioral disturbance thought to be due to substance abuse.
32. Has a DSM-5 defined substance abuse or dependence disorder (excluding nicotine and caffeine) within three months of screening.
33. Has a history of seizure disorder beyond childhood or is receiving treatment with any anticonvulsant to prevent seizures.

34. Has an untreated or uncompensated clinically significant renal, endocrine, hepatic, respiratory, gastrointestinal, psychiatric, neurologic, cardiovascular, hematological, immunological or cerebrovascular disease, malignance, allergic disease or other chronic and/or degenerative process at screening.
35. Has any clinically significant abnormal laboratory, VS, physical examination, or 12-lead safety ECG findings at screening or changes from baseline that may interfere with the interpretation of PK or safety parameters or, in the opinion of the investigator, would make the participant inappropriate for entry into this study.
36. Is at imminent risk of self-harm, based on clinical interview and responses on the C-SSRS, or of harm to others in the opinion of the investigator. Participants must be excluded if they report suicidal ideation with intent, with or without a plan or method (e.g., positive response to item 4 or 5 in assessment of suicidal ideation on the C-SSRS) in the past 2 months or suicidal behavior in the past 6 months.
37. Is a WOCBP who has a positive serum pregnancy test at the screening visit or a urine pregnancy test within 48 hours before the first dose of study intervention. If the urine test is positive or cannot be confirmed as negative, a serum pregnancy test will be required.
38. Has a history of cancer (malignancy).

Exceptions: (1) Participants with adequately treated nonmelanomatous skin carcinoma or carcinoma in situ of the cervix may participate in the study; (2) Participants with other malignancies which have been successfully treated ≥ 10 years prior to the prestudy (screening) visit where, in the judgment of both the investigator and treating physician, appropriate follow-up has revealed no evidence of recurrence from the time of treatment through the time of the prestudy (screening) visit (except those cancers identified at the beginning of this exclusion criteria); or (3) Participants, who, in the opinion of the study investigator, are highly unlikely to sustain a recurrence for the duration of the study.
39. Has a clinically significant history or presence of sick sinus syndrome, first, second, or third degree atrioventricular (AV) block, myocardial infarction, pulmonary congestion, cardiac arrhythmia, prolonged QTc interval, or conduction abnormalities.
40. Has history of repeated or frequent syncope, vasovagal episodes, or epileptic seizures.
41. Has a family history of sudden death.
42. Has a history of any illness that, in the opinion of the study investigator, might confound the results of the study or poses an additional risk to the participant by their participation in the study.

43. Participant has an estimated creatinine clearance (CrCl) \leq 80 mL/min based on the Cockcroft-Gault (CG) Equation.

Cockcroft-Gault Equation:

$$\text{ClCr} = \frac{(140 - \text{age}[\text{yr}])(\text{body wt}[\text{kg}])}{(72)(\text{serum creat}[\text{mg/dL}])}$$

When creatinine is measured in micromole/litre, use this formula:

$$\text{ClCr} = \frac{(140 - \text{age}[\text{yr}])(\text{body wt}[\text{kg}])}{(72)(\text{serum creatinine}[\text{micromol/L}] \times 0.0113)}$$

For females, multiple the result by 0.85.

At the discretion of the investigator a measured creatinine clearance, as determined by a 24-hour urine collection, may be used in place of, or in conjunction with, the estimate of the creatinine clearance.

Participants who have a measured creatinine clearance of up to 10% below 80 mL/min may be enrolled in the study at the discretion of the investigator.

44. Has a history of significant multiple and/or severe allergies (e.g., food, drug, latex allergy), or has had an anaphylactic reaction or significant intolerability (i.e., systemic allergic reaction) to prescription or non-prescription drugs or food.
45. Is positive for hepatitis B surface antigen, hepatitis C antibodies or HIV.
46. Had major surgery, donated or lost 1 unit of blood (approximately 500 mL) within 4 weeks prior to the prestudy (screening) visit.

Prior/Concomitant Therapy

47. Has received treatment with clozapine for schizophrenia or treatment with monoamine oxidase inhibitors within 3 months of screening. Participant in Panel C has received a total daily dose of risperidone $>$ 6 mg.
48. Has received a parenteral depot antipsychotic medication within 3 months of pre-trial (screening).
49. Is unable to refrain from the use of co-medication with a moderate or strong inhibiting or inducing effect on [REDACTED] and/or [REDACTED] beginning approximately 2 weeks or 5 half-lives, whichever is longer, prior to administration of the initial dose of trial drug and throughout the trial or is unable to refrain from the use of sensitive substrates of [REDACTED]. Unable to refrain from cyclic hormone replacement therapy. There may be certain medications that are permitted (see Section 6.5).

Prior/Concurrent Clinical Study Experience

50. Has participated in another investigational study within 4 weeks (or 5 half-lives, whichever is greater) prior to the prestudy (screening) visit. The window will be derived from the date of the last visit in the previous study.

Diagnostic Assessments

51. Has history or presence of risk factors for TdP (e.g., cardiac disease, heart failure, hypokalaemia or hypomagnesaemia, hypertrophy, cardiomyopathy, or family history of long QT syndrome). Plasma calcium must be in within normal limits at screening and serum calcium must be within normal limits prior to dosing.

Other Exclusions

52. Is under the age of legal consent.
53. Has been in incarceration or imprisonment within three months prior to screening.
54. Consumes greater than 3 glasses of alcoholic beverages (1 glass is approximately equivalent to: beer [354 mL/12 ounces], wine [118 mL/4 ounces], or distilled spirits [29.5 mL/1 ounce]) per day. Participants who consume 4 glasses of alcoholic beverages per day may be enrolled at the discretion of the investigator.
55. Consumes excessive amounts, defined as greater than 6 servings (1 serving is approximately equivalent to 120 mg of caffeine) of coffee, tea, cola, energy drinks, or other caffeinated beverages per day.
56. Is a regular user of cannabis, any illicit drugs or has a history of drug (including alcohol) abuse within approximately 3 years. Participants must have a negative UDS prior to randomization.
57. Presents any concern by the investigator regarding safe participation in the study or for any other reason the investigator considers the participant inappropriate for participation in the study.
58. Is or has an immediate family member (eg, spouse, parent/legal guardian, sibling, or child) who is investigational site or Sponsor staff directly involved with this study.

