Scheduled Day	Screening	-6	-2	-1	1	2	3	4	5	6	7	8	9	10	11	12	13	14	15	16	17	18	19	20	21	~27			
Vital Signs (respiratory rate, temperature)	X			X					X					X							X						X	Complete predose; Day 5: Panel A only	
12-lead Safety ECG (Panels A and B only) ^e	X				X	X			X			X		X			X			X					X		X	Days 2, 5: Panel A only	
24-hour Holter ECG & Extraction (Panels A and B only) ^f				X							X			X			X			X		X	X						
12-lead Safety ECG (Panel C only) ^g	X				X							X		X	X		X	X		X				X			X	X	
Serum β-Human Chorionic Gonadotropin (β-hCG; WOCBP only)	X																											X	
Urine Pregnancy test (WOCBP only) ^h				X ^m																									
Serum Follicle Stimulating Hormone (FSH; WONCBP only)	X																												
HIV, hepatitis B and C Screen (per site SOP)	X																												
Urine Drug Screen (per site SOP) ⁱ	X			X																									
Laboratory Safety Tests (hematology, urinalysis, chemistry)	X			X ^m					X					X							X							X	Collected predose after ~8 hour fast
Columbia Suicide Severity Rating Scale (C-SSRS)-Baseline Version	X																												

Panels A, B and C																											
Study Period	Screening	Wash-out																							Post-study	Notes	
Scheduled Day	Screening	-6	-2	-1	1	2	3	4	5	6	7	8	9	10	11	12	13	14	15	16	17	18	19	20	21	~27	
Columbia Suicide Severity Rating Scale (C-SSRS)- Since Last Assessment Version ^j			X ^m							X					X				X					X		X	Complete predose
Barnes Akathisia Rating Scale (BARS) ^{j, k}			X ^m								X						X			X				X			Complete predose
Abnormal Involuntary Movement Scale (AIMS) ^{j, k}			X ^m								X						X			X				X			Complete predose
Simpson Angus Scale (SAS) ^{j, k}			X ^m								X						X			X				X			Complete predose
Bond and Lader Visual Analog Scale (VAS) ^j			X ^m			X			X			X					X			X				X			Days 2, 5, 11: Panel A only. Complete predose
Brief Psychiatric Rating Scale (BPRS; Panels B and C only) ^j	X		X ^m								X						X			X				X			Complete predose
AE/SAE review	X-----X																										
Biomarkers																											
Blood for Genetic Analysis ⁿ						X																					Collect predose from enrolled participants only; See Section 8.8
Pharmacokinetics																											
Blood for Plasma MK-8189 and/or Metabolites assay ^l						X		X			X		X	X		X	X		X	X		X					

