5.1.2 Panel B, Panel C and Panel D (Participants with Schizophrenia) Inclusion Criteria

Participants are eligible to be included in the study only if all of the following criteria apply:

10. Is in good health based on laboratory safety tests obtained at the screening visit. Appendix 2 provides a table of laboratory safety tests to be performed. Appendix 9 provides an algorithm for the assessment of out of range laboratory values.
11. Have a Body Mass Index (BMI) ≥ 18.5 and ≤ 40 kg/m², inclusive, and total body weight of ≥ 50 kg (110 lbs) at the screening visit. See Section 8.3.2 for criteria on rounding to the nearest whole number. BMI = weight (kg)/height (m)².
12. Have no clinically significant abnormality on 12-lead safety ECG performed at the pre-trial (screening) visit and/or prior to randomization. The assessment prior to randomization is based on the mean of the triplicate measures. Note: The QTcF duration must be <450 msec for males and <470 msec for females, the QRS duration <120 msec and the PR interval <200 msec. Repeat 12-lead safety ECGs may be performed in participants whose parameters are, per investigator discretion, minimally outside the designated range. Appendix 8 provides a table of the 12-Lead Electrocardiogram Abnormality Criteria.
13. Have a normal resting blood pressure (systolic blood pressure is ≥ 90 mm Hg and ≤ 140 mmHg; diastolic blood pressure is ≥ 60 mmHg and ≤ 90 mmHg) and normal resting heart rate (≥ 45 beats per minute [bpm] and ≤ 100 bpm) in the semi-recumbent position at the pre-trial (screening) visit and/or prior to randomization. Repeat evaluations may be done if the values for a participant are, per investigator discretion, minimally outside the designated range. The assessment prior to randomization is based on the mean of the triplicate measures. For Panel C and Panel D, participants may be included if values are outside the normal range but considered not clinically significant per investigator discretion.
14. Meets diagnostic criteria for schizophrenia or schizoaffective disorder according to the Diagnostic and Statistical Manual of Mental Disorders (DSM-5) criteria with the onset of the first episode being no less than 2 years prior to screening and monotherapy with antipsychotics for treatment should be indicated.
15. Has a total Brief Psychiatric Rating Scale (BPRS) score of < 48 with a BPRS score < 4 for #10 (hostility) and #14 (uncooperativeness) at the screening visit.

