Participants who have a measured creatinine clearance of up to 10% below 80 mL/min may be enrolled in the study at the discretion of the investigator.

15. Has a history of significant multiple and/or severe allergies (e.g., food, drug, latex allergy), or has had an anaphylactic reaction or significant intolerability (i.e., systemic allergic reaction) to prescription or non-prescription drugs or food.
16. Is positive for hepatitis B surface antigen, hepatitis C antibodies or HIV.
17. Had major surgery, donated or lost 1 unit of blood (approximately 500 mL) within 4 weeks prior to the prestudy (screening) visit.

Prior/Concomitant Therapy

18. Is unable to refrain from or anticipates the use of any medication, including prescription and nonprescription drugs or herbal remedies, beginning approximately 2 weeks (or 5 half-lives) prior to administration of the initial dose of study drug, throughout the study (including washout intervals between treatment periods), until the poststudy visit. There may be certain medications that are permitted (see Section 6.5).

Prior/Concurrent Clinical Study Experience

19. Has participated in another investigational study within 4 weeks (or 5 half-lives, whichever is greater) prior to the prestudy (screening) visit. The window will be derived from the date of the last visit in the previous study.

Diagnostic Assessments

20. Has history or presence of risk factors for TdP (e.g., cardiac disease, heart failure, hypokalaemia or hypomagnesaemia, hypertrophy, cardiomyopathy, or family history of long QT syndrome). For Panel A, plasma calcium must be within normal limits at screening and serum calcium must be within normal limits prior to dosing.

Other Exclusions

21. Is a smoker and/or has used nicotine or nicotine-containing products (e.g., nicotine patch and electronic cigarette) within 3 months of screening.

22. Is under the age of legal consent.
23. Consumes greater than 3 glasses of alcoholic beverages (1 glass is approximately equivalent to: beer [354 mL/12 ounces], wine [118 mL/4 ounces], or distilled spirits [29.5 mL/1 ounce]) per day. Participants who consume 4 glasses of alcoholic beverages per day may be enrolled at the discretion of the investigator.
24. Consumes excessive amounts, defined as greater than 6 servings (1 serving is approximately equivalent to 120 mg of caffeine) of coffee, tea, cola, energy drinks, or other caffeinated beverages per day.

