10.2 Appendix 2: Clinical Laboratory Tests

- The tests detailed in [Table 6](#) will be performed by the local laboratory.
- Protocol-specific requirements for inclusion or exclusion of participants are detailed in Section 5 of the protocol.
- Additional tests may be performed at any time during the study as determined necessary by the investigator or required by local regulations.
- Pregnancy testing:
 - Pregnancy testing requirements for study inclusion are described in Section 5.1.
 - Pregnancy testing (urine or serum as required by local regulations) should be conducted at the end of relevant systemic exposure and correspond with the time frame for female participant contraception in Section 5.1.
 - Additional serum or urine pregnancy tests may be performed, as determined necessary by the investigator or required by local regulation, to establish the absence of pregnancy at any time during the subject's participation in the study.

Table 6 Protocol-required Safety Laboratory Assessments

Laboratory Assessments	Parameters			
Hematology	Platelet Count	WBC count with Differential: Neutrophils Lymphocytes Monocytes Eosinophils Basophils		
	RBC Count			
	Hemoglobin			
	Hematocrit			
Chemistry	Blood Urea Nitrogen (BUN)	Potassium	Aspartate Aminotransferase (AST)/ Serum Glutamic-Oxaloacetic Transaminase (SGOT)	Total bilirubin (and direct bilirubin, if total bilirubin is elevated above the upper limit of normal)
	Albumin	Bicarbonate	Chloride	Phosphorous
	Creatinine	Sodium	Alanine Aminotransferase (ALT)/ Serum Glutamic-Pyruvic Transaminase (SGPT)	Total Protein
	Glucose (fasting)	Calcium	Alkaline phosphatase	
Routine Urinalysis	Specific gravity pH, glucose, protein, blood, ketones, [bilirubin, urobilinogen, nitrite, leukocyte esterase] by dipstick Microscopic examination (if blood or protein is abnormal)			

Laboratory Assessments	Parameters
Other Screening Tests	Follicle-stimulating hormone (as needed in women of nonchildbearing potential only) Urine alcohol, cotinine (Panel A only) and drug screen (to include at minimum: amphetamines, barbiturates, cocaine, opiates, cannabinoids and benzodiazepines; If the clinical site's drug screen evaluation routinely detects additional agents, the relevance of positive findings for exclusion will be discussed with the Sponsor.) Serum or urine β human chorionic gonadotropin (β hCG) pregnancy test (as needed for WOCBP) Serology (HIV antibody, hepatitis B surface antigen [HBsAg], and hepatitis C virus antibody)

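### Hypomagnesaemia is an exclusion in all four panels, but no protocol-required test measures magnesium, so finding it depends on history and optional tests

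*Combined protocol and SAP*

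**What the plan says.** Criterion 51 (Section 5.2.2) excludes a participant who "Has history or presence of risk factors for TdP (e.g., cardiac disease, heart failure, hypokalaemia or hypomagnesaemia" and further conditions. Criterion 20 (Section 5.2.1) has the same list for healthy participants, again naming "hypokalaemia or hypomagnesaemia". Both cover a past history and a current presence.

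One electrolyte also receives an explicit requirement. In criterion 51 it reads: "Plasma calcium must be in within normal limits at screening and serum calcium must be within normal limits prior to dosing". Criterion 20 has an equivalent sentence for Panel A.

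For the laboratory basis of eligibility, the inclusion criteria say: "Appendix 2 provides a table of laboratory safety tests to be performed". That table is headed "Protocol-required Safety Laboratory Assessments". The Schedule of Activities for each set of panels has one row for these tests, "Laboratory Safety Tests (hematology, urinalysis, chemistry"), at screening, at Day -2 or Day -1 depending on the panel, during treatment and post-study. Appendix 9 then sets out how out-of-range values are handled and allows entry when every protocol-specified value is normal.

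**The concern.** Hypomagnesaemia is by definition a laboratory finding: a low blood magnesium. The protocol names it as a risk factor for Torsade de Pointes and excludes its presence, yet the required laboratory panel does not measure it. The exclusion is therefore in force on paper, and Section 5 permits no waivers, but nothing in the required procedures checks its current-presence part.

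The study exists partly to assess QTc. Section 2.1 promises a rigorous evaluation, Panel D escalates to 48 mg, and Panel C participants stay on an atypical antipsychotic in a protocol that itself notes that many antipsychotics prolong QT. At stake are the cardiac safety of a participant whom the plan means to keep out, and whether a stated eligibility rule can be verified.

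**Working it through.** The plan gives no figure to reproduce, and there is no arithmetic behind the point. The check sets the exclusion against each place where a magnesium result might be required.

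1. **The exclusion.** Criteria 20 and 51 name two electrolyte disorders, hypokalaemia and hypomagnesaemia, and add a calcium requirement.

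2. **The required chemistry list.** Table 6 has 15 analytes: blood urea nitrogen, albumin, creatinine, fasting glucose, potassium, bicarbonate, sodium, calcium, AST, chloride, ALT, alkaline phosphatase, total bilirubin, phosphorous and total protein. The grid reads as complete and shows no redaction.

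| Electrolyte | Role in criteria 20 and 51 | Required assay in Table 6 | Explicit limit in the criterion |
|---|---|---|---|
| Potassium | Low value named as a risk factor | Yes | None stated |
| Calcium | Must be normal at screening and before dosing | Yes | Normal limits |
| Magnesium | Low value named as a risk factor | No | None stated |

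3. **The schedule.** The Schedule of Activities lists hematology, urinalysis and chemistry. Neither schedule (Panels A to C, Panel D) has a separate magnesium or electrolyte row.

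4. **The entry algorithm.** Appendix 9 acts on protocol-specified laboratory values. Magnesium is not one of them, so no branch of the algorithm asks for it. Appendix 9 does not override criteria 20 and 51, but it supplies nothing with which to apply this part of them.

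5. **Any other mention.** The only other reference to magnesium is magnesium hydroxide, an example of a permitted antacid in Section 6.5.

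6. **Routes that remain.** A past history can be found under Section 8.1.4. For current presence, Appendix 2 lets the investigator order additional tests, Section 8 allows further evaluations for participant safety and the use of qualifying routine-care results, and Section 8.12 lets tests be added to blood already drawn. All are optional, and none names magnesium.

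Potassium and calcium each have a required assay behind them. Magnesium has none, in any panel at any visit.

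**The case against.** The strongest reply is that the criterion can still be applied. A reader might infer from Table 6 that hypomagnesaemia cannot be established at all. The documents do not support that, because the optional routes in Section 8, Section 8.12 and Appendix 2 are real. This part of the reply stands, and it limits the point to a missing requirement.

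A second reply is that the list in criteria 20 and 51 is illustrative and judged by the investigator, and that other items on it, such as cardiomyopathy, have no dedicated test either. This stands in part. Those items can at least be approached through the required history, examination and ECG, whereas a low blood magnesium is defined by the one result that the plan does not ask for.

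Third, a reader might infer that undetected cases would distort the QTc findings. The documents do not support more than a small effect. Section 9.4 analyses QTc as change from baseline, and Panels A, B and D have a time-matched Day -1 Holter, so a stable pre-existing effect is largely subtracted. Confounding would need magnesium to shift during confinement on standardised meals. Other safeguards also apply: entry limits on QTcF (below 450 msec for males and 470 msec for females), exclusion of prolonged QTc, and rules in Section 8.3.4 for repeat ECGs and monitoring. These reduce the consequence of a missed case but do not detect it.

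Fourth, a reader might infer from "serum calcium must be within normal limits prior to dosing" that calcium is the only laboratory gate. It is not: creatinine clearance, hepatitis and HIV serology, pregnancy tests and the urine drug screen are all explicit. Calcium is only the sole electrolyte with a stated limit.

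**Conclusion.** The point holds as an internal mismatch. The protocol excludes current hypomagnesaemia in all four panels, about 64 planned participants (16 + 16 + 12 + 20), and requires no test that would reveal it. Detection rests on medical history and investigator discretion.

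No size can be given in terms of affected participants. The documents state no frequency, and dividing one hypothetical case by a group size would say nothing about how often it occurs. The case rests on participant safety and an enforceable criterion. It does not rest on bias in the exploratory QTc analysis, whose model is in a separate plan that is not available here.

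The practical reach is narrower than 64. Sections 2.1 and 4.2 report tolerability data from Panels A and B, and Section 4.3.1 cites tolerability in Panels A, B and C to support the Panel D starting dose. A change now would mainly reach Panel D, up to 20 participants at the highest doses. The conclusion assumes that no document outside the review, such as the procedures manual, already requires magnesium. If one does, Table 6 still needs to say so. This is worth correcting, but it does not undermine the trial.

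**What to change.** Add serum magnesium to the Table 6 chemistry list at screening and at the existing pre-dose laboratory draw (Day -2 or Day -1, according to panel). Refer criteria 20 and 51 to that result, so that the exclusion, the laboratory table and Appendix 9 agree. The sponsor should state how the result is to be read against the criterion; no threshold is proposed here.

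Limiting the text to a known history would also reconcile the documents. It would give up the current-presence exclusion, so it is the weaker remedy.

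The cost is one more analyte, assumed to run on the existing sample, and possibly a few more screen failures. If a separate tube were needed, volume would not be an obstacle. Appendix 10 gives 288 mL for Panel D, the highest total. With the optional 50 mL this is 288 + 50 = 338 mL, which leaves 500 - 338 = 162 mL under the limit in Section 8. Two further collections, even at the full 12.5 mL laboratory volume, would use 2 x 12.5 = 25 mL.
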